## 4.2. Inclusion/Exclusion Criteria

### 4.2.1. Inclusion Criteria

Eligible patients in the analyses must meet each of the following criteria:

- 18 years of age or older
- 4 or more inpatient hospital visits across Atrium Health Metro hospitals in 2019

### 4.2.2. Exclusion Criteria

- Existing MVP participants (enrolled in the 2019 MVP program cohort)
- Patients who at the time of identification for the MVP program are
  - Actively enrolled in a Levine Cancer Institute oncology navigation program
  - Actively receiving hospice or palliative care
  - Attributed to a primary care provider at an outside healthcare system (e.g. Novant)
- Patients whose primary residence is skilled nursing facility

## 4.3. Evaluable Population

Patients included in the evaluable population for this project, will have their data inform the final outcomes assessment. All patients who meet the inclusion and exclusion criteria in both groups will be assessed for the primary outcome (intent to treat).

AH Care Management will enroll patients assigned to the 2020 MVP program cohort on a predetermined date, flagging the MVP program participants as “active” in the care management’s data application (PatientPing).

## 5. OVERALL DESIGN

### 5.1. Variables

#### 5.1.1. Primary Outcome Variable

The primary outcome variable is the number of inpatient (IP) hospital encounters over a 12-month period.

- IP encounter is defined as an admission to an AH acute care hospital.

### 5.1.2. Secondary Outcome Variables

- The number of IP hospital encounters over a 6-month period.

All secondary outcome variables listed below are cumulative over 6-month and 12-month periods.

- Combined number of IP and OBS hospital encounters at AH hospitals
- Combined number of IP and OBS hospital encounters at both AH + non-AH hospitals
- Among patients with at least 1 encounter during the study period, 30-day all-cause non-elective inpatient readmission rate to any AH hospital
- Among patients with at least 1 encounter during the study period, 30-day all-cause non-elective inpatient readmission rate to the same AH hospital as the index encounter
- Emergency Department encounters
- Mortality
- Hospital bed days (IP)
  - This is the total length of stay (LOS) in days (discharge date – admission date) for acute care inpatient utilization.
- Cost of Care - Hospital charges
  - Total accrued hospital billed charges for inpatient encounter at Atrium Health primary enterprise acute care facilities.

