### 1.3. Secondary Objectives

The Secondary Objectives are to

(1) evaluate the effect(s) of participation in the MVP program on:

- 6-month inpatient hospital utilization
- 6-month and 12-month Combined IP and OBS hospital stays at Atrium Health facilities
- 6-month and 12-month Combined IP and OBS hospital stays at AH and other facilities
- 6-month and 12-month IP hospital stays that are readmission eligible (using CMS criteria)
- 6-month and 12-month 30-day readmission rate among patients who had at least one encounter during the time frame
- 6-month and 12-month ED visit rate
- 6-month and 12-month Mortality rate
- 6-month and 12-month Hospital bed days (length of stay, IP)
- 6-month and 12-month Hospital charges

(2) assess variability in MVP program treatment effects associated with predefined patient and program factors, including:

- insurance status
- age, gender, race and ethnicity
- English as second language
- type of care management program (e.g., ACM, etc.)
- community characteristics
- clinical characteristics (e.g., CCI)

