### 5.1.4. Main Explanatory Variable of Interest: Intervention Identifier

The MVP program is the intervention (treatment group).

Bivariate identifier variable = 1 if the patient was randomly assigned to the MVP program and is flagged “active” in PatientPing Care Management application; 0 otherwise

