### 5.2. MVP Program - Intervention Description

Population Health's Multiple Visit Patient (MVP) care management program aims to manage health and lower hospital utilization among patients with a history of high inpatient hospital stays at Atrium Health. Patients eligible for the program have four or more inpatient visits over the 12-month period prior to enrollment. Once enrolled, each MVP program participant receives on-going support from an assigned MVP care manager and larger care management team, including the following core program components:

- customized care plan developed for each patient at the time of enrollment
- routine, virtual health monitoring and collaborative care management team-based review
- personalized navigation and coordination across multidisciplinary Atrium Health services, as needed
- education, health coaching, and support via telephonic and in-person interactions, as needed

**Screening and care manager assignment.** A list of patients with four or more inpatient hospital visits in 2019 will be pulled from the Atrium Health electronic data warehouse (EDW). The care management team will review eligibility for the MVP program. The list of eligible participants will be randomized using parallel block randomization approach into the 2020 MVP program cohort (intervention) and the control group.

Eligibility for the program is based on past utilization, with patients with 4 or more inpatient visits over a 12-month period qualifying for the program. To identify the new MVP cohort, the list of patients with highest volume of inpatient hospital visits is generated by Clinical Analytics. The care management leadership team then reviews the chart of each patient on the list to determine eligibility and assigns the patient to the appropriate care management group. The number of patients accepted to the MVP program is constrained by the care management group's capacity. Existing MVP enrollees continue to receive care from their currently assigned team. Patients are assigned to a distinct care management group based on insurance/care needs:

- i. Ambulatory Care Management (ACM)
  - Commercial insurance

- Medicare only
  - Medicare with Medicaid as second
  - Uninsured outside of Mecklenburg and Union counties
  - Non CA II Medicaid
- ii. Community Care Partners (CCP)
    - Medicaid CA II
      - a. Priority list (determined by the Medicaid state program)
      - b. Provider preferred
    - Community Care of NC (CCNC)

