## 6.2. Statistical analysis

Analyses will include all patients meeting the inclusion and exclusion criteria. All analyses will follow the intention-to-treat (“ITT”) principle, such that patients will be analyzed based on the assignment of their primary care site to the MVP program or usual care.

Descriptive statistics will be calculated to screen all variables for accuracy and to examine distributions. Balance in baseline characteristics between the groups will be assessed.

The primary and secondary outcomes will be estimated as functions of *Treatment* (intervention / MVP program identifier) covariates  $X$ :

$$Y_i = \beta_0 + \beta_1 (\text{Treatment}) + \beta_2 X_i + \varepsilon_i$$

where

- $\beta_1$  is the parameter of interest and measures the Intent to Treat: the causal effect of being randomized into the treatment group (in this study we expect the intent to treat and treatment to be almost the identical).
- $X$  are covariates, uncorrelated with Treatment, but they can aid in the precision of the estimate;  $\beta_2$  are the corresponding parameter estimates. The covariates will include patient's demographic and clinical characteristic, past utilization, insurance type, type of program management, community characteristics, care management groups, and discharge location.

Generalized linear models will be used. Results will be presented as marginal effects (continuous and count outcomes) and odds ratios (binary outcomes). Wald test will be used to assess the statistical significance of the independent variable. The level of significance is set to 0.05. Appropriate model diagnostics will be performed on each model to assess fit. Data will be analyzed using SAS Enterprise Guide 7.1 (SAS Institute Inc., Cary, NC, USA) and the R programming environment.

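### The two 30-day readmission rates use only patients with an encounter after randomisation, so the intention-to-treat causal label in 6.2 does not fit them

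*Combined protocol and SAP*

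**What the plan says.** Section 5.1.2 lists two readmission outcomes, each cumulative over 6 and 12 months. The first is "Among patients with at least 1 encounter during the study period, 30-day all-cause non-elective inpatient readmission rate to any AH hospital". The second has the same restriction and is the "30-day all-cause non-elective inpatient readmission rate to the same AH hospital as the index encounter". Section 1.3 restricts in slightly different words: "30-day readmission rate among patients who had at least one encounter during the time frame". The Protocol Summary (Study Objectives) lists readmissions at 6 and 12 months with no restriction.

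Under 6.3, data accrue over 365 days from enrolment, so the qualifying encounter comes after randomisation. Section 1.1 hypothesises fewer inpatient stays, and 5.2 says that the program "aims to manage health and lower hospital utilization among patients with a history of high inpatient hospital stays at Atrium Health". Section 1.3 also makes the number of readmission-eligible stays an outcome, so the plan itself treats the pool of index stays as something assignment may change.

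Section 6.2 makes no exception for readmission. It says "Analyses will include all patients meeting the inclusion and exclusion criteria", puts primary and secondary outcomes into one model, and describes the treatment coefficient as "the causal effect of being randomized into the treatment group".

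**The concern.** Randomisation makes the full arms comparable. It does not make comparable the subsets who later have an encounter, if assignment affects who that is. Suppose the program keeps some patients out of hospital altogether. They leave the MVP denominator while their counterparts stay in the usual-care denominator. If those patients differ in readmission risk from the rest, the two retained groups differ before any effect on readmission is considered.

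Section 6.2 presents the covariates as unrelated to treatment and useful for precision. That holds in the randomised arms. After selection on a later event it need not hold, and adjustment removes only the part of the imbalance that the measured covariates capture.

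At stake are four secondary analyses (two outcomes at two time points) that a reader of 6.2 would take as randomised comparisons.

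**Working it through.** **Plan's own figure.** The only sample-size result is 295 per group in 6.1. It reproduces: 2 × (1.960 + 0.842)² × 0.45² / 0.104² = 294, or 295 with the t distribution, and 454 × 0.65 = 295. It concerns inpatient encounters. The plan gives no readmission rate and no share of patients expected to have an encounter, so everything below except the two means is assumed.

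**Does assignment change who is retained?** The means from 6.1 are 6.5 × (1 − 0.436) = 3.67 for usual care and 6.5 × (1 − 0.54) = 2.99 for MVP, a ratio of 0.816. I treat them as 12-month means and halve them for 6 months. With a negative binomial count and the same dispersion k in both arms, the share with no admission is (k/(k+m))^k.

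| k | 12 months, MVP vs usual care | 6 months, MVP vs usual care |
|---|---|---|
| 0.8 | .288 vs .253 | .430 vs .386 |
| 1.61 | .185 vs .148 | .347 vs .294 |
| 2.75 | .132 vs .097 | .303 vs .246 |
| Poisson | .050 vs .026 | .224 vs .160 |

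The arms differ by about 2.5–3.7 points at 12 months and 4.5–6.4 at 6 months. The values 1.61 and 2.75 come from a variance of (0.45 × 6.5)² = 8.56 at each arm's mean, treating the baseline count as constant.

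**What does that do to the readmission contrast?** I simulated gamma-distributed patient risk, admissions uniform in time, a readmission as a gap of 30 days or less, and no deaths. An encounter was read as an inpatient stay and the rate as the proportion with any readmission. Entries are MVP minus usual care in percentage points, for k = 1.61 / 2.75. Repeat runs agree within about 0.3 points.

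| Assumed effect | 12 months, with an encounter | 12 months, all randomised | 6 months, with an encounter | 6 months, all randomised |
|---|---|---|---|---|
| Uniform | −6.8 / −7.9 | −7.5 / −8.7 | −5.9 / −6.3 | −6.1 / −6.7 |
| Higher-risk half only, same total fall | −7.4 / −8.3 | −6.7 / −8.0 | −7.3 / −7.7 | −6.2 / −7.0 |
| Rate ratio 0.50 in lower-risk half, same total fall | −3.6 / −5.3 | −8.4 / −9.9 | −1.8 / −2.2 | −5.5 / −6.1 |
| Lower-risk half only (0.50) | −0.4 / −3.1 | −5.8 / −8.1 | +1.7 / +0.1 | −3.0 / −4.3 |

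An intermediate case (0.70 in the lower-risk half, same total fall) is diluted by 1.2–1.8 points. In the last row, readmissions counted per randomised patient fall 6–11%, while per patient with an encounter they rise 1–9%.

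**Bias in a defined group.** The table compares two denominators, so its gaps are not a measure of bias. A direct benchmark is patients who would have an encounter under either arm. Let a0 and a1 be the shares with an encounter under usual care and MVP. Let rA be the readmission rate in the benchmark group and rP the rate in patients whose encounters MVP prevents. With no effect in the benchmark group and no patient gaining an encounter through MVP, the MVP arm shows rA and usual care shows [a1·rA + (a0 − a1)·rP]/a0. With k = 2, rA = 30% and rP = 10%: (.839 × .30 + .036 × .10)/.875 = .292, a spurious 0.8 points against MVP. Across Poisson to k = 0.5 and rP of 0–10%, the range is 0.5–1.5 points. It is zero if rP = rA, and 5.0 points if the share with an encounter fell from 80% to 60%.

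**Does adjustment restore balance?** With a baseline score correlated 0.3, 0.5 or 0.7 with risk (assumed), 89–92%, 72–76% or 49–52% of the risk imbalance remains.

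**Precision.** The 95% half-width is 1.96 × √(2 × .45 × .55/n). With n equal to 61–85% of 295 or 454, it is 7.0–10.3 points.

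**The case against.** Conditional readmission rates are a standard measure, and the restriction is visible in the definition. A reader might infer from the lower-risk rows that the planned analysis will hide a real benefit. The documents do not support that. Section 5.2 describes contact driven by use: alerts on admission or ED attendance, monthly review of patients with a recent acute encounter, and generally no calls after a month without a hospital stay. That makes benefit in higher-risk patients at least as plausible, and there the conditional result is not diluted. If assignment changes nobody's encounter status, there is no selection at all, and if the program has no effect on anything the test remains valid.

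Two further limits stand. The all-randomised change includes the fall in admissions itself, so it differs from the conditional change even when the effect is uniform. And 5.1.2 does not say which encounters qualify; if observation or ED contacts count, fewer patients drop out of the denominator.

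It is also fair that readmissions per randomised patient answer a different question from post-discharge performance, and that they overlap with the inpatient count. This argues for keeping the conditional rate as a description. It does not make the label in 6.2 correct.

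**Conclusion.** The point holds as a mismatch between the defined outcomes and the effect claimed for them. It follows from the text and needs no assumed number. For both readmission outcomes, at 6 and 12 months, the coefficient is not the intention-to-treat effect, and the statement that all eligible patients are analysed is not met.

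Size and direction cannot be fixed from the documents. In the assumed scenarios, the conditional and all-randomised results agree within about 1 point for a uniform effect, and there is no dilution for benefit in higher-risk patients. The proportion readmitted is clearly attenuated only when benefit is concentrated in lower-risk patients. It reverses only at 6 months, when that half alone benefits. The largest gap in the table is 5.4 points (−0.4 against −5.8), below the half-width of 7–10 points.

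A reader might also infer that the trial's main result is compromised. It is not: the primary outcome is the inpatient count, which 4.3 assesses in all eligible patients in both groups. The change is worth making because it is cheap and these results would otherwise be reported as randomised comparisons.

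**What to change.** 1. In 6.2, exempt the conditional readmission rates from the intention-to-treat sentence and from the statement about who is analysed, and report them as descriptive.
2. Align 5.1.2 with 1.3 so that the qualifying encounter falls within the same 6- or 12-month window as the rate. State which encounter type qualifies, and reconcile both sections with the unrestricted entry in the Protocol Summary.
3. Add to 1.3 and 5.1.2, as the intention-to-treat readmission comparison, the number of 30-day readmissions per randomised patient (zero if never admitted), by assigned arm, at 6 and 12 months. Do this for any AH hospital and, if wanted, for the same AH hospital. Show deaths by arm beside it.

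The cost is a few lines of text and two to four added analyses from utilisation and mortality data that section 6 already collects. The added count overlaps with the inpatient count, falls when admissions fall even if post-discharge performance is unchanged, and is lowered by early death. Relocation by arm should not be required: section 6 lists no such data, and 5.4 mentions relocation only as a reason for leaving the MVP program. The activity flag in the treatment identifier (5.1.4) and the handling of death and relocation in the other count outcomes are separate matters.

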### 5.1.3. Exploratory Outcome variables

All exploratory outcome variables listed below are cumulative over 6-month and 12-month periods

- Primary care visits and primary care visits scheduled but not kept (no shows)
- Healthy Days at Home
  - This is a measure of quality of life (Burke, et al. 2019). It measures the number of days spent at home during a predefined time period.
- Cost of Care - Paid Amount for the Medicare patient subgroup

### 5.1.4. Main Explanatory Variable of Interest: Intervention Identifier

The MVP program is the intervention (treatment group).

Bivariate identifier variable = 1 if the patient was randomly assigned to the MVP program and is flagged “active” in PatientPing Care Management application; 0 otherwise

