      - a. Medicaid CA II that are not being managed by CCP (ie Mecklenburg, Union, Anson counties)
- iii. Community Care Bridge (CCB)
    - Uninsured in Mecklenburg and Union counties
  - iv. Advanced Illness Management (AIM)
    - Patients with a limited prognosis but for whom hospice is not yet an option.  
This program is part of Continuing Care.

**Program Start Point.** Patients in the intervention group are enrolled in the MVP program at one time point determined by Care Management leadership. The start point is marked by an “Active” indicator in the Patient Ping app. From that point, the assigned care manager starts receiving “pings,” which are real time updates alerting the care manager about the MVP patient’s hospital utilization (IP, OBS, ED). The MVP care manager checks on the patient, communicates with providers and helps coordinate care and the transition to home.

**Initial Assessment and Customized Plan.** Shortly after the program start date, each MVP care manager calls patients assigned to her/him to conduct a full assessment. The case manager continues to try to reach the patient, and there is no limit for the number of attempted phone calls over a period of time. The assessment contains review of medications, upcoming appointments, social determinants of health (living arrangements, financial), and a PHQ9 survey. The care manager assesses a patient’s motivation to change, provides education, solicits questions about health, and how the patient wants to be contacted. The care manager uses the assessment to create a customized plan for each patient.

**MVP program features:** Care managers are alerted via Patient Pings when a patient is admitted to hospital or has an ED encounter.

- If a patient is admitted to a hospital, the care manager consults the inpatient case manager and calls the patient if needed
- During monthly huddles, care management reviews charts of patients who had an acute care encounter during the past 30 days.
- In general, if a patient had 0 hospital stays in the previous month, care managers do not make any calls.
- There are no home visits.

- Face-to-face visits may take place if the patient is admitted to a facility at a close proximity to the care manager.

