## 6.3. Data Collection Dates

All participants in the MVP cohort will be enrolled at the same time and flagged as “active” status in the PatientPing application. Data accrual will take place during 365 days from the date of patient enrollment.

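### The treatment variable is coded by randomisation plus an active flag, so an unflagged MVP patient would be analysed as usual care despite the stated intention-to-treat analysis

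*Combined protocol and SAP*

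**What the plan says.** Section 5.1.4 defines the main explanatory variable. It equals 1 "if the patient was randomly assigned to the MVP program and is flagged “active” in PatientPing Care Management application; 0 otherwise".

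Section 6.2 uses that variable, the "intervention / MVP program identifier", as Treatment in the regression for the primary and secondary outcomes. It says that its coefficient "measures the Intent to Treat: the causal effect of being randomized into the treatment group" and adds that "in this study we expect the intent to treat and treatment to be almost the identical". Sections 4.3 and 6.2 both state that the analysis is by intention to treat.

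Three places describe how the flag is set:
- 4.3: "AH Care Management will enroll patients assigned to the 2020 MVP program cohort on a predetermined date", with participants flagged active in PatientPing.
- 5.2, on the program start point: "Patients in the intervention group are enrolled in the MVP program at one time point determined by Care Management leadership". The flag marks that start.
- 6.3: "All participants in the MVP cohort will be enrolled at the same time and flagged as" active in PatientPing.

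On the unit of assignment, 4.1 and 5.2 randomise individual patients from a list, 1:1 and stratified by programmatic subgroup. The intention-to-treat sentence in 6.2, however, analyses patients by the assignment of their primary care site.

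**The concern.** Under intention to treat, a patient's group is fixed at randomisation. The rule in 5.1.4 adds a second condition that is met only afterwards, when Care Management activates the patient. A patient randomised to MVP who is not flagged fails that condition and takes the same code as usual care. Such patients leave the MVP group and also join the comparison group. If their admission rate differs from that of the rest, the coefficient is no longer the effect of being randomised, and the error can go in either direction. The same variable serves the primary and the secondary outcomes, so the problem would run through all of them.

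The intention-to-treat sentence in 6.2 does not supply a working rule in its place, because it refers to site assignment and this trial assigns no sites.

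**Working it through.** **The plan's own figures.** This point challenges none of them, and those used here reproduce. Section 6.1 has 454 randomised per arm and 35% attrition: 454 × 0.65 = 295.1, as stated. For a difference of 0.104, SD 0.45 and two-sided 0.05, n = 2 × (1.960 + 0.842)² × 0.45² / 0.104² = 294 per group by the normal approximation. Power at 295 is 0.80, as stated.

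**Coding rule against estimand.**

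| Patient | Code under 5.1.4 | Group under intention to treat |
|---|---|---|
| Randomised to MVP, flagged | 1 | MVP |
| Randomised to MVP, not flagged | 0 | MVP |
| Randomised to usual care | 0 | Usual care |

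Only the second row disagrees, so the whole effect depends on how many patients fall in it. The documents give no number.

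**Illustration on the admission ratio.** Assumptions: no true effect; 454 per arm; mean admissions scaled to 1 in each randomised arm; k MVP patients unflagged, p = k/454; unflagged patients have c times the average count.

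- Coded-1 mean = (1 − pc)/(1 − p)
- Coded-0 mean = (1 + pc)/(1 + p)
- Ratio = coded-1 mean / coded-0 mean; a correct analysis gives 1.00

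For k = 23, p = 23/454 = 0.0507. With c = 0 the ratio is (1/0.9493)/(1/1.0507) = 1.107. With c = 1.5 it is (0.9240/0.9493)/(1.0760/1.0507) = 0.950.

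| Unflagged k | Share | Coded 1 v coded 0 | c = 0 | c = 0.5 | c = 1 | c = 1.5 |
|---|---|---|---|---|---|---|
| 0 | 0% | 454 v 454 | 1.000 | 1.000 | 1.000 | 1.000 |
| 5 | 1.1% | 449 v 459 | 1.022 | 1.011 | 1.000 | 0.989 |
| 23 | 5.1% | 431 v 477 | 1.107 | 1.052 | 1.000 | 0.950 |

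A ratio above 1 makes MVP look harmful, and one below 1 makes it look beneficial. If the unflagged are typical (c = 1) there is no shift at any share.

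**Illustration on the scale of the power calculation.** Take 295 per arm and SD 0.45, and assume that a share f is unflagged and differs from the average by half an SD, g = 0.225, in mean percentage decrease. With no programme effect the absolute shift is g × [f/(1 − f) + f/(1 + f)].

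- f = 1%: 0.225 × (0.0101 + 0.0099) = 0.005; two-sided type I error 0.052
- f = 5%: 0.225 × (0.0526 + 0.0476) = 0.023; standard error 0.45 × √(1/280.25 + 1/309.75) = 0.0371; type I error 0.093

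Both f and g are assumed.

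**Site wording.** Sections 4.1, 5.1.4 and 5.2 all make the patient the unit of randomisation, and no site allocation is described. This contradiction in wording has no numerical effect of its own.

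**The case against.** The strongest reply is that, under the described procedure, the flag nearly restates assignment. The whole assigned cohort is to be activated on one date. Activation comes before the first call, so it does not depend on reaching the patient. Under 5.4, declining to participate, hospice or palliative care, and a move to a nursing home do not end participation. The usual selective route, in which refusers drift into the control group, is therefore largely closed. The intended estimand is also plain from 6.2, and covariate adjustment might absorb part of any shift. The ratios above are unadjusted, whereas 6.2 will report marginal effects for counts.

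Most of this stands as a limit on the likely size, and large unflagged shares would not fit the plan. It does not remove the contradiction:
- Section 4.1 randomises to MVP referral. Activation follows at a time chosen by Care Management leadership, and no maximum gap is given. Death, relocation or an administrative omission could fall in between.
- Section 6.2 expects only near agreement between assignment and treatment, and no section says how the remaining patients are coded.
- Section 5.1.4 does not say when the flag is read, and section 6 retrieves data retrospectively. Under 5.4, participation ends on death, relocation or incarceration. The documents do not say whether the flag is then removed. If it were, and were read late, the coding would depend on events after randomisation, including mortality, which is a secondary outcome.

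It is also fair to say that the site phrase is editorial and adds no weight to the coding point.

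**Conclusion.** The concern holds. As written, the coding rule contradicts the stated intention-to-treat analysis, and no fallback to randomised assignment is given. That conclusion rests on the text and is firm. The numerical consequence is conditional. It is nil if all MVP patients are flagged and the flag is fixed at the start. It is about 1 to 2% on the admission ratio with 5 patients unflagged, and runs from 0.95 to 1.11 with 23 unflagged, for c between 1.5 and 0. The unflagged share and c are assumptions, and these figures illustrate the mechanism without predicting its size. The point should be fixed because the rule can give a wrong answer for the primary outcome and correcting it costs almost nothing.

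**What to change.** - In 5.1.4, define Treatment as 1 if the patient was randomised to MVP and 0 if randomised to usual care, regardless of PatientPing status.
- In 6.2, replace the reference to the primary care site's assignment with the arm to which the patient was individually randomised.
- Report how many MVP-assigned patients were not flagged on the start date. Use the flag only to describe uptake or in a supplementary analysis labelled as such.

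The first two items are one sentence each. No new data, additional patients or change of sample size is needed, and nothing is lost if flagging proves complete.
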